13.6.1 End-of-Stage-2 Follow-up

The End-of-Stage-2 Follow-up marks the end of the study participation and is a telephone/teleconference follow-up which must be performed by the PI at the latest two weeks after occurrence of one of the following:

- 1. The participant has reported a total of five treated attacks in Stage 2, implying that all the devices received at Site Visit 2 have been used.
- 2. 12 months have passed since the participant's inclusion in Stage 2.
- 3. The participant no longer wishes to participate or is lost to follow up.

The PI must during the telephone/teleconference follow-up interview collect and record in the eCRF the following information: subjective satisfaction, side effects, non-reported adverse events, any other comments the participant has about the treatment and study participation, as well as the DASS-21 questions (cf. document *PAREMA1 Case Report Form content*). The patient should return unused Stage 2 devices by mail or at the site.

13.7 Randomization

The participants will be randomized in a 1:1 ratio to use either the active or sham device in Stage 1.

Participants and investigators will be blinded with respect to which device (active or sham) each participant will use or has used. The randomization scheme will be generated by study biostatisticians using permuted block randomization prior to the start of the clinical trial and implemented through the randomization module in the EDC. Randomization will be stratified by site, and each site will have a separate randomization scheme using random predetermined block sizes.

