10.3.1 Number of subjects and duration of study

A minimum of 174 participants and a maximum of 220 participants will be randomized in this clinical study at up to 15 sites in the EU and the United States. The enrolment of participants is intended to start in Q1 of 2023 and continue until the target number has been enrolled ("*Last Patient In Stage 1*" (LPIS1)), which is estimated to occur in Q2 of 2025. From the point of LPIS1, there will be a period of six months until conclusion of Stage 1 for all participants ("*Last Patient Out Stage 1*" (LPOS1)), estimated to occur in Q4 of 2025.

Individual participants will participate in Stage 1 until either of the following conditions are met:

- 1. The participant has treated and reported four attacks
- 2. The overall conclusion of Stage 1 (six months after LPIS1)
- 3. The participant no longer wishes to participate or is lost to follow up.

Participants meeting condition 1 or 2 will after concluding Stage 1 have the option of continuing in Stage 2 (open-label extension) which has a maximum duration of 12 months. Individual participants will participate in Stage 2 until either of the following conditions are met:

- 1. The participant has used all five devices received when starting Stage 2
- 2. 12 months have passed since the participant's inclusion in Stage 2.
- 3. The participant no longer wishes to participate or is lost to follow up.

The study is concluded when all participants have concluded Stage 2 (*"Last Patient Out Stage 2"* (LPOS2)).

The maximum estimated duration of total participation for an individual participant (Stage 1 + Stage 2) is 27 months.

10.3.2	Measures	to	minimize bias	
--------	----------	----	---------------	--

Design Attribute	Justification
Prospective	A prospective study design will eliminate the bias associated with case selection in a retrospective review and will ensure that identical procedures are followed for data capture and review.
Multi-centre	Inclusion of multiple study centres will reduce the impact of bias associated with any one investigator, clinic population, or geography.
Randomized	Randomization will minimize selection bias and minimize differences in demographic variables.

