### 1.5 Power and sample size calculation

#### 1.5.1 Assumptions

The estimated study size of 200 to 240 included participants has been determined on the basis of data from the pilot study (Fuglsang et al., 2018) and post-market data collected in Denmark, Sweden and Germany from 2018 to 2020.

To estimate the sample size for this trial, it was assumed that 12% of subjects in the sham group and 30% of subjects in the active group would experience PF2. For AMSP2, a 26% response rate in the sham group and a 61% response rate in the active group was assumed.

The primary statistical test for this analysis will be a  $\chi^2$  significance test adjusted for clustered data (using the methods of Donner and Banting (Donner and Banting, 1988)) since subjects could contribute more than one migraine attack. The intraclass correlation coefficient (ICC) from preliminary data on this device was 0.486. This is a group-sequential design with one interim analysis, so the O'Brien Fleming Spending function will be used to set significant thresholds of 0.0052 at the interim analysis and 0.048 at the final analysis.

Power and sample sizes were estimated via simulation using the above parameters for a  $\chi^2$  significance test adjusted for clustered data. These simulations assumed a third of subjects would have one migraine attack during the course of the study, a third of subjects would have two study attacks, and a third of subjects would have three study attacks. In the interim analysis, a more refined method of estimating number of attacks per participant will be employed, using the observed attack frequencies from the interim data (cf. section 1.4). Additionally, it was expected that 22% of subjects would drop out of the trial and 10% of attacks would have missing data at the 2 hour time point, for a total of 32% of randomized subjects that would not provide data usable for the statistical analysis of the primary or secondary endpoint.

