#### 1.7 Outcomes and Analysis

#### 1.7.1 Primary hypothesis

In line with earlier studies on aura-phase treatment (Bates D. et al., 1994; Olesen J. et al., 2004), the trial's **primary end point** will be absence of moderate or severe pain at 2 hours (AMSP2), ), i.e. the percentage of study attacks in which the participant reported absence of headache of moderate/severe intensity at 2 hours post-treatment initiation. "Study attacks" are all attacks treated and reported during Stage 1, apart from the first attack which is a training attack and is not included in the analysis.

The intention-to-treat (ITT) analysis set will be used for the primary effectiveness hypothesis test. The primary effectiveness hypothesis is:

 $H_0: p_{Rehaler} = p_{sham}$ 

 $H_a: p_{\text{Rehaler}} \neq p_{\text{sham}}$ 

Where:

pRehaler = proportion of attacks in the Rehaler group with AMSP2

psham = proportion of attacks in the sham group with AMSP2

The primary effectiveness hypothesis will be tested using a two-sided adjusted  $\chi^2$  test for clustered binary data (Donner and Banting, 1988) at a 5% level of significance.

If Pearson's chi-squared test statistic is written as  $\chi^2 = \sum_{i=1}^{G} \chi_i^2$  with G = the number of treatment groups, then the adjusted  $\chi^2$  approximately follows a chi-squared distribution with G-1 degrees of freedom and is calculated as follows (Donner and Banting, 1988):

$$\chi_A^2 = \sum_{i=1}^G \frac{\chi_i^2}{\overline{C_i}}$$

Where:

- $\overline{C}_{l} = \sum_{j=1}^{n_{i}} \frac{m_{ij}C_{ij}}{\sum m_{ij}}$
- $C_{ij} = 1 + (m_{ij} 1)\rho$
- G is the number of treatment groups
- ni is the number of individuals in group i
- ρ is the correlation coefficient between any two responses in the same individual
- mij denotes the number of observations for individual j in group i

The corresponding 95% confidence interval for the difference in proportion of attacks with AMSP2 between the Rehaler and sham groups will also be calculated as follows (Donner and Klar, 1993):

95% Confidence Interval:  $(\hat{p}_{Rehaler} - \hat{p}_{sham}) \pm 1.96 * \widehat{SE}(\hat{p}_{Rehaler} - \hat{p}_{sham})$ 

Where:

- $\hat{p}_{Rehaler}$  = observed proportion of attacks in the Rehaler group with AMSP2
- $\hat{p}_{sham}$  = observed proportion of attacks in the sham group with AMSP2

• 

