| Categorical      | 
 
Headache Score at 2 hours (HS2)
 
Most Bothersome Symptom Score at 2 hours (MBS2)
 
Functional Disability Score at 2 hours (FDS2)
 
Participant Satisfaction at 48 hours (PS48)
 
Light Sensitivity Score at 2 hours (LSS2)
 
Nausea Score at 2 hours (NS2)
 
Sound Sensitivity Score at 2 hours (SSS2)
 
 | Ordinal logistic regression using the
proportional odds model with device type
(active or sham) as the exposure variable.
Threshold p value: 0.05   |

Table 3: Hypothesis testing for primary and secondary endpoints

The following Stage 2 exploratory endpoints will be compared to corresponding baseline values reported at Site Visit 1:

- How many times in the past month has the participant taken respectively a prescription acute migraine drug or an over-the-counter acute analgesic, with the intention to treat migraine.
- Proportion of patients who used an opioid drug to treat migraine the past month
- Proportion of patients who have been hospitalized for migraine in the past month

All hypothesis tests will be performed on the ITT data set of attacks. In the resulting data set each attack will constitute a data point and each patient will constitute a cluster including from one to three data points. The statistical analysis will take clustering into account by using the adjusted  $\chi^2$  statistic for clustered binary data developed by Donner and Banting (Donner and Banting, 1988) and validated by others (Gonen et al., 2001; Jung et al., 2001). This method negates the risk of type I errors that is incurred if clustering is disregarded. In the event that changes are made to the statistical analysis plan, these changes will be submitted for approval to the Competent Authorities.

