# 1.8 Homogeneity Across Study Sites

The homogeneity of the treatment effect across study sites will be evaluated using a generalized linear mixed model where device used and site are fixed effects and each patient is a random effect (cluster). Homogeneity of the treatment effect between subjects in the United States and subjects outside the United States will also be evaluated using a generalized linear mixed model. If heterogeneity is detected, exploratory analyses will be conducted, which may include adjusting analyses for baseline characteristics that significantly differ across sites.

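### Site is a randomisation stratum and baseline predictors are collected, but the AMSP2 and PF2 tests use neither: the test is valid but forgoes some precision, mainly for PF2

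*Protocol*

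**What the plan says.** **Allocation.** Protocol 13.7: "The participants will be randomized in a 1:1 ratio to use either the active or sham device in Stage 1", and "Randomization will be stratified by site, and each site will have a separate randomization scheme", using permuted blocks. Protocol 10.3.1 allows "up to 15 sites in the EU and the United States"; the synopsis estimates 6 in Europe and 7 in the USA, so 13.

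**Tests.** SAP 1.7.1: "The primary effectiveness hypothesis will be tested using a two-sided adjusted" chi-square for clustered binary data (Donner-Banting). The statistic and its confidence interval contain only the two group proportions, the numbers of participants and attacks, and a within-participant design effect. Protocol 10.2 and 16.1 name the same test. SAP 1.7.3 gives PF2 the same method and thresholds as AMSP2, and says of all the tests: "The statistical analysis will take clustering into account by using the adjusted" statistic. Table 3 of the SAP names an ordinary Pearson chi-square where the text below it names the clustered one. That is a separate matter, since neither version has a site or covariate term.

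**Where site and baseline data do appear.** SAP 1.8 plans a mixed model in which "device used and site are fixed effects and each patient is a random effect (cluster)", but only to assess homogeneity of effect. Baseline adjustment is mentioned there as an optional exploratory step if heterogeneity is found. Protocol 11.4.1 uses attack frequency, headache days, Migraine-ACT, DASS-21 and prophylaxis status only for exploratory correlations with AMSP2 and PF2.

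**The concern.** Blocking within site forces the arms to be balanced within site. If sites differ in response rate, the between-site part of the variance cannot contribute to the arm difference, yet an unstratified test still counts it as error. Its standard error is then somewhat too large. Prognostic baseline variables that are left out of the test stay in the error term in the same way.

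PF2 is where this could matter. The trial is sized on it (SAP 1.3 and 1.5), and it is the first step after AMSP2 in the fixed sequence (SAP 1.7.2 and 1.7.3), so a miss on PF2 stops every later labelling claim. SAP version 1.1 raised the minimum from 174 to 200 and the maximum from 220 to 240 to gain power, and SAP 1.4 calls 240 the largest feasible study. Precision that needs no further participants is therefore worth having.

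**Working it through.** **Inputs from the documents.** PF2 12% sham and 30% active; AMSP2 26% and 61%; intraclass correlation 0.486; final threshold 0.048; one, two or three study attacks in equal thirds; 32% without usable data (all SAP 1.5.1). At 200 randomised, 136 are evaluable, 68 per arm (SAP Table 1). Protocol 16.2 instead assumes two attacks per participant.

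**Step 1: the plan's own figure.** SAP Table 1 gives PF2 85.5% and AMSP2 99.1% at 200. Each arm has 68 × 2 = 136 attacks.
- Two attacks each: design effect 1 + 0.486 = 1.486, effective n = 136/1.486 = 91.5 per arm. PF2 power 85.0%, AMSP2 99.9%.
- Equal thirds with 1, 2 and 3 attacks: design effect (1 + 2 × 1.486 + 3 × 1.972)/6 = 1.648, effective n = 82.5. PF2 power 81.1%, AMSP2 99.7%.

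The PF2 figure reproduces with two attacks each. With the SAP's own split it is lower, which is why the simulations below start near 82%.

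**Step 2: baseline covariates.** The share of variance explained, R², is not in the documents, so 2-10% is assumed. Formula: power = Φ(θ/√(1−R²) − z), with z = 1.977 for two-sided 0.048 and θ = 1.977 + 1.058 = 3.035 for the stated 85.5%.

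| R² (assumed) | PF2 power | Gain, points | Equivalent saving of 200 | AMSP2 power |
|---|---|---|---|---|
| 0 | 85.5% | – | – | 99.1% |
| 2% | 86.2% | 0.7 | 4 | 99.2% |
| 5% | 87.2% | 1.7 | 10 | 99.3% |
| 10% | 88.9% | 3.4 | 20 | 99.5% |

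Simulation (13 sites, permuted blocks, 136 participants, 1-3 attacks, 3,000 trials per case) compared the planned test with a risk-difference regression on site and one baseline score, using participant-robust variance. PF2 power went from 81.5 to 83.3% (R² about 4.5%), 84.2 to 84.8% (about 4%) and 82.0 to 85.6% (about 9%). With a useless score it went from 81.8 to 81.4%. The simulation error of a single power figure is about √(0.82 × 0.18/3000) = 0.7 points. At R² 10% the confidence interval has √0.9 = 0.95 of its unadjusted width.

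**Step 3: site alone.** The spread between sites is also not in the documents. Four sets of simulations used the same layout and differed in the assumed site effect. SD is the between-site standard deviation on the marginal logit scale.

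| Set | Site effect (assumed) | Size of planned test (nominal 0.048) | PF2 power, planned to site-adjusted | Gain, points |
|---|---|---|---|---|
| A | none | 0.051 | 81.8 to 81.7 | −0.1 |
| A | 5% of latent between-participant variance | 0.051 (run with a covariate also present) | 80.8 to 80.7 | −0.1 |
| B | none | – | 81.7 and 81.8 | about 0 |
| B | SD 0.5 | 0.044 | 80.9 to 82.3 | 1.4 |
| B | SD 0.7 | 0.041 | 80.7 to 83.0 | 2.3 |
| C | none | 0.046 | 81.4 to 82.3 | 0.9 |
| C | SD 0.5 | 0.045 | 82.8 to 84.0 | 1.2 |
| C | SD 0.7 | 0.045 | 82.3 to 83.9 | 1.6 |
| D | none | 0.048 | 82.3 to 83.1 | 0.8 |
| D | SD 0.5 | 0.042 | 82.0 to 83.6 | 1.6 |
| D | SD 0.7 | 0.038 | 82.0 to 85.0 | 3.0 |

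In sets C and D, 0.8-0.9 points of gain appear with no site effect at all. There the site-adjusted test rejected slightly too often under the null (0.050-0.052 in C, 0.051-0.055 in D, against 0.048), so that part comes from the variance estimator. Net of it, the gain is 0.3 and 0.7 points in C, and 0.8 and 2.2 in D. With A at zero and B at 1.4-2.3, the part attributable to site is about 0 to 2 points.

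**The case against.** The case for leaving the test alone is substantial, and most of it stands.

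- **The primary endpoint loses almost no power.** A reader might infer that the AMSP2 test is weakened. SAP Table 1 already gives it 99.1%, and adjustment at R² 10% adds 0.4 points. Only the interval width improves.
- **The test is valid.** A reader might infer that ignoring the strata undermines the type I error. The error runs the other way: where sites differ, size is at or below nominal. It is the adjusted test, without a small-sample correction, that comes out slightly liberal.
- **The gains are not documented quantities.** A reader might take 1-2 points from site as established. The documents give neither a between-site spread nor an R², and nothing in them shows that attack frequency, headache days or prophylaxis use predict PF2. With a modest site effect the gain was nil.
- **The data are thin for a large model.** PF2 would have about 136 × 0.12 + 136 × 0.30 = 57 events, or about 35 after dividing by 1.648. Thirteen site terms, three covariates and device make 17 parameters, and 136/13 is about 10 evaluable participants per site. Unpooled site terms would be fragile.

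What does not stand is that SAP 1.8 already covers this. Its site model assesses homogeneity and changes neither test, and its baseline adjustment is optional and conditional. The balance of risk still favours adjusting: about 0.4 points lost if the covariate is useless, against roughly 1 to 3.5 gained if it explains 2-10%.

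**Conclusion.** The concern holds as a matter of efficiency. The design stratifies by site and collects usable predictors before randomisation, and neither enters the AMSP2 or PF2 test. For AMSP2 the benefit of adjusting is a somewhat narrower confidence interval. For PF2 it is about 0 to 2 points of power from site (assumed SD 0 to 0.7) and about 1 to 3.5 points from covariates (assumed R² 2-10%). Agreement between design and analysis is a reason to include site even if the power gain proves to be nil. The documents do not support reading this as a bias, a false-positive risk or a shortage of power for the primary endpoint. The textual facts are certain; the sizes are only as good as the assumed site spread and R², and the simulated covariate gains come from a linear risk-difference regression rather than the logistic model suggested below.

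**What to change.** Before final unblinding, amend Protocol 10.2 and 16.1 and SAP 1.7.1 and 1.7.3 so that AMSP2 and PF2 are tested with one named model. A suitable choice is a logistic GEE with independence working correlation, clustered on participant, containing:
- device;
- site, with sites below a prespecified minimum size pooled by country;
- attack frequency of migraine with aura, headache days per month, and prophylaxis (yes/no), all as recorded at Site Visit 1.

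Report a standardised risk difference with a participant-robust variance that has a small-sample correction. Keep the Donner-Banting test as supportive. Leave out regulator setting, treatment delay and pain at treatment start, which Protocol 11.4.1 lists alongside the baseline factors but which are measured after randomisation. State in SAP 1.4 which test the interim analysis and sample size re-estimation use.

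No new data are needed. The cost is a pooling rule, the variance correction, amended wording in both documents, and submission of the SAP change to the Competent Authorities, as SAP 1.7.3 requires.

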13.8 Treatment Unblinding

Blinding of individual study participants can be broken in circumstances of medical emergency where knowledge of blinded treatment is necessary. In such cases, the randomization codes will be broken and the PI must be unblinded with regards to the participant in question. Upon unblinding of a study participant, Stage 1 will be prematurely ended for this participant and site will call in for Site Visit 2 and participant will be transferred to Stage 2, if agreed to by the participant. If necessary to break the blind, the involved competent authority (if applicable) and EC/IRB will be informed. The procedure of unblinding is further described in Safety Management Plan for the study. In addition to emergency unblinding, the code for the individual participant will also be broken at conclusion of Stage 1 and study participant will at site visit 2 be informed of their study allocation during Stage 1.

13.9 Concomitant Medications

For this study, a prescription medication is defined as a medication that can be prescribed only by a properly authorized/licensed clinician. Relevant medications to be reported in the eCRF are concomitant prescription medications and over-the-counter medications.

Medication usage will be documented for medications a participant is currently taking at the time of the screening visit, and any medication stopped within the previous thirty (30) days, and for medication changes (started, stopped, or change of dose/frequency) through to study exit.

Participants should, if possible, refrain from using rescue medication for at least the first two hours after the initiation of treatment with the study device during Stage 1. "Rescue medication" is here defined as the following:

- Prescription or OTC pharmaceuticals that have migraine as an indication for use
- OTC painkillers/analgesics, including acetaminophen/paracetamol, aspirin, ibuprofen and naproxen
- Neurostimulators for pain treatment

Any use of rescue medications within 48 hours from initiation of treatment will be documented via the ePRO app.

Additionally, any medication that is determined by the investigator to be a potential safety issue or concern, and/or any medication taken in connection with treatment for an adverse event (AE) will be documented.

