12.1 Eligibility

12.1.1 Inclusion criteria

Participants must meet all of the following inclusion criteria:

- 1. Participant has migraine with typical aura (ICHD3 classification 1.2.1)² with the additional criterion that historically in more than 75% of cases of aura a **moderate or severe** headache begins between 10 and 60 minutes after aura onset.
- 2. Participant has had 3 or more migraine-with-aura attacks over the last six months.
- 3. Participant is 18 to 65 years of age.
- 4. Participant's age at onset of migraine with aura was less than 50 years.
- 5. If participant is taking migraine prophylactic drugs, the dose must have been stable for three months or more.
- 6. Participant agrees to withhold usual acute migraine medications until at least two hours after treatment with the study device.
- 7. Participant does not plan to initiate new (and/or change existing) migraine prophylaxis medication for the duration of Stage 1 of the study.
- 8. For female participants: is willing to use adequate contraception during study participation
- 9. Participant owns a smartphone compatible with the ePRO study diary app.
- 10. Participant agrees to use the study device as intended, comply with all study requirements including treatment, follow-up visits, and recording required study data in the ePRO app.
- 11. Participant is willing and able to provide written informed consent.

²Migraine without Aura (MO) is NOT an exclusion criterion. Patients with Aura (MA) very often also have MO.

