12.1.2 Exclusion criteria

Participants must meet none of the following criteria:

- 1. Participant has a history of chronic pulmonary disease (e.g. Chronic Obstructive Pulmonary Disease (COPD) or pulmonary fibrosis).
- 2. Participant has a history of severe cardiovascular disease (e.g. symptomatic coronary artery disease, prior myocardial infarction, congestive heart failure) or cerebrovascular disease (e.g. prior stroke or transient ischemic attack, symptomatic carotid artery disease, prior carotid endarterectomy or other vascular neck surgery).
- 3. Participant has a history of intracranial hyper/hypo-tension.
- 4. Participant has a history of cerebral aneurysm.
- 5. Participant has had previous brain surgery, including stenting.
- 6. Anaemia, defined as a hemoglobin concentration in capillary blood lower than 11 g/dL
- 7. Participant has a baseline S_{PO2} level which is lower than 95%
- 8. Participant has 15 or more headache days per month
- 9. Participant has medication-overuse headache (ICHD3 classification 8.2).
- 10. Participant has a known history or suspicion of recurring secondary headache which in the opinion of the investigator may interfere with the study.
- 11. Hemiplegic migraine
- 12. Participant has other significant and relevant pain problem (e.g. cancer pain, fibromyalgia or other head or facial pain disorders)
- 13. Participant has a known history or suspicion of substance abuse or addiction (within the last 5 years) that in the opinion of the investigator may confound the study assessments.
- 14. Participant has a history of psychiatric or cognitive disorder and/or behavioural problems which in the opinion of the investigator may interfere with the study.
- 15. Participant belongs to a vulnerable population or has any condition such that his or her ability to provide informed consent, comply with the follow-up requirements, or provide self-assessments is compromised (e.g. homeless, developmentally disabled, prisoner).
- 16. For female participants: is pregnant or actively trying to become pregnant.
- 17. Participant is participating in any other clinical investigation or has participated in an interventional clinical trial in the preceding 30 days.
- 18. Participant has any condition that according to the investigator may pose the participant at risk or provide confounding data.
- 19. Participant is unable, as perceived by study personnel, to correctly understand and follow the instructions for use of the device and ePRO app.

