- Miscellaneous baseline information (e.g. self reported height and weight, ethnicity, Most Bothersome Symptom during MA attacks, currently and previously used migraine drugs, questions regarding efficacy of current acute treatment, evaluation of depression, anxiety and stress via the DASS-21 (Depression Anxiety Stress Scales 21 item questionnaire))

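### Section 13.9 defines rescue medication by a list with no catch-all, so prescription opioids or analgesics without a migraine indication do not count as rescue in Res24, SPF24 and FR48; the effect is probably small

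*Protocol*

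**What the plan says.** Protocol section 13.9 introduces rescue medication as a definition and gives three items:

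- "Prescription or OTC pharmaceuticals that have migraine as an indication for use"
- "OTC painkillers/analgesics, including acetaminophen/paracetamol, aspirin, ibuprofen and naproxen"
- neurostimulators used for pain

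The examples in the second item are open-ended, but only within over-the-counter products. The section then says that rescue use in the first 48 hours is captured in the ePRO app. Section 13.10.6 has the app ask about rescue medication at 2, 24 and 48 hours.

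The term is used in these places:

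- Protocol section 11.3: Res24 counts attacks with rescue between 2 and 24 hours. SPF24 and FR48 require pain freedom at 2 hours, no rescue and no relapse.
- Protocol section 11.4.1: exploratory endpoint 17, rescue use before 2 hours.
- Protocol section 16.8.3 and SAP section 1.6.3: the per-protocol set drops attacks with rescue before 2 hours.

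SPF24, Res24 and FR48 are third, seventh and twelfth among the secondary endpoints in the labelling sequence (SAP sections 1.7.2 and 1.7.3).

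Elsewhere, Protocol section 8.1 names opioids among current acute treatments. Section 11.4.2 counts opioid use for migraine in Stage 2, and SAP section 1.7.3 compares that with baseline: "Proportion of patients who used an opioid drug to treat migraine the past month". The Stage 2 drug-use questions (Protocol sections 11.4.2, 13.6 and 13.10.11) go by the purpose for which the drug was taken, not by its label.

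**The concern.** A participant who takes a prescription opioid, or a prescription analgesic not labelled for migraine, to end a Stage 1 attack has been rescued in any clinical sense. Under section 13.9 that attack is unrescued. Nothing in the protocol or SAP widens the list, and no rule brings the eCRF medication record into the attack-level endpoints.

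Two errors could follow. Res24 would miss such attacks. SPF24 and FR48 could count some of them as sustained successes. These endpoints may support labelling claims, so what counts as rescue should be settled before anyone sees results by arm.

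**Working it through.** **Text check.** A prescription opioid without a migraine indication fails item 1 (no indication), item 2 (not over the counter) and item 3 (not a device). An attack is miscoded only if every rescue taken in it is off the list; one listed drug as well is enough to code it correctly.

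**Inputs.** The plan states no rate or power for Res24, SPF24 or FR48, so there is no figure of its own to reproduce. From SAP sections 1.5.1 and 1.5.2: 136 evaluable participants, one third each with 1, 2 and 3 study attacks, ICC 0.486, PF2 30% active and 12% sham. From SAP Table 3: two-sided threshold 0.05 for these endpoints. All rescue rates and unlisted shares below are assumptions, as is using ICC 0.486 for these endpoints.

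**Effective size.** Design effect = (1×1 + 2×1.486 + 3×1.972)/6 = 1.648. Effective attacks per arm = 136×2/1.648/2 = 82.5.

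**Calibration.** With the pooled normal approximation at 0.048, this gives PF2 power of 81.1% (SAP Table 1: 85.5%) and AMSP2 power of 99.7% (SAP: 99.1%). The powers below are therefore approximate.

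**Res24.** Recorded rate = true rate × (1 − unlisted share). Assumed true rescue is 40% active and 60% sham, with the same unlisted share in both arms:

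| Unlisted share | Recorded active / sham | Difference (points) | Power |
|---|---|---|---|
| 0% | 40.0 / 60.0 | 20.0 | 73.3% |
| 1% | 39.6 / 59.4 | 19.8 | 72.4% |
| 2% | 39.2 / 58.8 | 19.6 | 71.6% |
| 5% | 38.0 / 57.0 | 19.0 | 68.9% |
| 20% | 32.0 / 48.0 | 16.0 | 55.6% |

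The standard error of the difference is √[(0.4×0.6 + 0.6×0.4)/82.5] = 7.6 points. Shares of 1 to 5% shift the difference by 0.2 to 1.0 points, or 0.03 to 0.13 standard errors. A 20% share shifts it by 4.0 points, about half a standard error. An equal share always pulls the difference towards zero and leaves equal true rates equal.

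**SPF24 and FR48.** A rescued attack can pass as a success by two routes.

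- Route A: pain-free at 2 hours, then a relapse between reports that is treated only with an unlisted drug and gone by the next report. Pain is rated at 1, 2, 24 and 48 hours. Added rate = PF2 rate × share of attacks on this path (assumed 10 to 30%) × unlisted share. At 10% and 1%: 0.03 against 0.012, so +0.02 points. At 30% and 5%: 0.45 against 0.18, so +0.27. At 30% and 20%: 1.80 against 0.72, so +1.08.
- Route B: an unlisted drug before 2 hours brings pain to zero and holds it there. Added rate = early rescue (assumed 5% active, 15% sham) × unlisted share × 30% sustained. At 1%: 0.015 against 0.045, so −0.03 points. At 5%: 0.075 against 0.225, so −0.15. At 20%: 0.30 against 0.90, so −0.60. Equal early use gives zero, and swapping the arms reverses the sign.

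The standard error is √[(0.15×0.85 + 0.06×0.94)/82.5] = 4.72 points at assumed rates of 15% and 6%, and 6.18 points at 30% and 12%. The largest shift at a 5% share is 0.27/4.72 = 0.06 standard errors; at a 20% share it is 1.08/4.72 = 0.23.

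**The case against.** The strongest reply is that no endpoint error is shown. The endpoints come from participants' ePRO answers, and the wording of the question is in the CRF content document, which is not among the documents reviewed. Nothing says that a yes is re-scored against the list. The Stage 2 questions go by purpose, so the Stage 1 form may as well. This stands as a limit: the error arises only if the form or the scoring follows section 13.9. It does not remove the point, because section 13.9 is the only definition given and the ePRO capture is described in the same term.

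The affected group is probably small. Exclusion criteria 9, 12 and 13 remove medication-overuse headache, other significant pain problems and substance abuse that could confound assessments. Some opioids or prescription analgesics may carry a migraine indication in some countries and so already count. This also stands.

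A reader might infer more than the documents support:

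- *That the protocol contradicts itself.* Inclusion criterion 6 reads "Participant agrees to withhold usual acute migraine medications until at least two hours after treatment with the study device", which would cover a participant's usual opioid. But it is an eligibility undertaking and does not define rescue or score an endpoint. It also makes route B less likely.
- *That Res24 could swing widely.* Unlisted shares of 20% active and 10% sham would record 22 points instead of 20; 10% and 20% would record 12. Such gaps need drug choice to differ by arm, and nothing in the documents points to that in a randomised, participant-blinded comparison.
- *That the definition favours the device.* Route A leans that way if more active attacks are pain-free at 2 hours. Route B can lean either way, so the net direction is unknown.
- *That the main result is at risk.* ITT AMSP2 and PF2 are scored from pain at 2 hours and keep attacks with early rescue.

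**Conclusion.** The point holds as a flaw in a stated definition. Applied as written, section 13.9 leaves out a class of acute treatment that the protocol itself recognises. Res24 would then under-count rescue, and SPF24 and FR48 could count some rescued attacks as successes.

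The size is unknown and probably small. At assumed unlisted shares of 1 to 5%, the shift is at most 0.13 standard errors for Res24 (equal shares) and 0.06 for SPF24 or FR48. These figures rest on assumed rescue rates, path shares and ICC.

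The consequence is further limited by the testing order. SPF24 is formally tested only after three rejections (AMSP2, PF2, MBSF2), Res24 only after seven, and FR48 last. The per-protocol repeat of the primary test is for the sponsor's information only (SAP section 1.9). Severity is minor.

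**What to change.** Before unblinding, define rescue in Protocol section 13.9 and in the SAP as any medication or neurostimulator taken to treat the migraine attack, regardless of labelled indication or prescription status. This is the purpose-based standard already used in Stage 2. Apply it to Res24, SPF24, FR48, exploratory endpoint 17 and the per-protocol set. State whether an anti-emetic taken only for nausea counts; that is a clinical decision, but it should be made in advance.

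Score from the participant's ePRO answer, without filtering by indication. The eCRF medication record can serve only as a partial check: it holds drugs in use or recently stopped at screening, and then entries "for medication changes (started, stopped, or change of dose/frequency) through to study exit", so as-needed doses may not appear.

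Change the ePRO question only if two things are true: it restricts answers to the section 13.9 list, and blinded, pooled Site Visit 1 data show that unlisted acute drugs are in use. That visit records "currently and previously used migraine drugs, questions regarding efficacy of current acute treatment", and the SAP relies on baseline opioid use from it. Otherwise correcting the text is enough. If the question does change, report a sensitivity analysis by wording.

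Costs: one definition in two documents, and submission of the SAP change to the competent authorities, as SAP section 1.7.3 requires. SPF24 and FR48 become slightly stricter. Enrolment was intended to start in Q1 2023, so attacks have probably been reported already; rewording the app now would leave two collection wordings and require telling participants. That is why it should be conditional.
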